Calcium (Ionized), Low (mg/dL; mmol/L)	<LLN to 4.0 <LLN to 1.0	3.6 to <4.0 0.9 to <1.0	3.2 to <3.6 0.8 to <0.9	<3.2 <0.8
Cardiac Troponin I, High	NA	NA	NA	Levels consistent with myocardial infarction or unstable angina as defined by the local laboratory
Creatine Kinase, High	3 to <6×ULN	6 to <10×ULN	10 to <20×ULN	$\geq$ 20×ULN
Creatinine, High  Report only one	1.1 to 1.3×ULN	>1.3 to 1.8×ULN OR Increase to 1.3 to <1.5×subject's Baseline	>1.8 to <3.5×ULN OR Increase to 1.5 to <2.0×subject's Baseline	$\geq$ 3.5×ULN OR Increase of $\geq$ 2.0×subject's Baseline

Laboratory Valuesk: Chemistries*				
Parameter	Grade 1 Mild	Grade 2 Moderate	Grade 3 Severe	Grade 4 Potentially Life-threatening
Creatinine Clearancem or eGFR, Low lReport only one	NA	<90 to 60 ml/min or ml/min/1.73 m  OR 10 to <30% decrease from subject's Baseline	<60 to 30 ml/min or ml/min/1.73 m  OR 30 to <50% decrease from subject's Baseline	<30 ml/min or ml/min/1.73 m  OR ≥50% decrease from subject's Baseline or dialysis needed
Glucose (mg/dL; mmol/L) Fasting, High	110 to 125 6.11 to <6.95	>125 to 250 6.95 to <13.89	>250 to 500 13.89 to <27.75	≥500 ≥27.75
Nonfasting, High	116 to 160 6.44 to <8.89	>160 to 250 8.89 to <13.89	>250 to 500 13.89 to <27.75	≥500 ≥27.75
Glucose, Low (mg/dL; mmol/L)	55 to 64 3.05 to <3.55	40 to <55 2.22 to <3.05	30 to <40 1.67 to <2.22	<30 <1.67
Lactate, High	ULN to <2.0×ULN without acidosis	≥2.0×ULN without acidosis	Increased lactate with pH <7.3 without life-threatening consequences	Increased lactate with pH <7.3 with life-threatening consequences
Lipase, High	1.1 to <1.5×ULN	1.5 to <3.0×ULN	3.0 to <5.0×ULN	≥5.0×ULN
Lipid Disorders (mg/dL; mmol/L) Cholesterol, Fasting, High	200 to <240 5.18 to <6.19	240 to <300 6.19 to <7.77	≥300 ≥7.77	NA
LDL, Fasting, High	130 to <160 3.37 to <4.12	160 to <190 4.12 to <4.90	≥190 ≥4.90	NA
Triglycerides, Fasting, High	150 to 300 1.71 to 3.42	>300 to 500 >3.42 to 5.7	>500 to <1,000 >5.7 to 11.4	>1,000 >11.4
Magnesiumn, Low (mEq/L; mmol/L)	1.2 to <1.4 0.60 to <0.70	0.9 to <1.2 0.45 to <0.60	0.6 to <0.9 0.30 to <0.45	<0.6 <0.30
Phosphate, Low (mg/dL; mmol/L)	2.0 to <LLN 0.65 to <LLN	1.4 to <2.0 0.45 to <0.65	1.0 to <1.4 0.32 to <0.45	<1.0 <0.32
Potassium, High (mEq/L; mmol/L)	5.6 to <6.0 5.6 to <6.0	6.0 to <6.5 6.0 to <6.5	6.5 to <7.0 6.5 to <7.0	≥7.0 ≥7.0
Potassium, Low (mEq/L; mmol/L)	3.0 to <3.4 3.0 to <3.4	2.5 to <3.0 2.5 to <3.0	2.0 to <2.5 2.0 to <2.5	<2.0 <2.0
Sodium, High (mEq/L; mmol/L)	146 to <150 146 to <150	150 to <154 150 to <154	154 to <160 154 to <160	≥160 ≥160
Sodium, Low (mEq/L; mmol/L)	130 to <135 130 to <135	125 to <130 125 to <130	121 to <125 121 to <125	≤120 ≤120
Uric Acid, High (mg/dL; mmol/L)	7.5 to <10.0 0.45 to <0.59	10.0 to <12.0 0.59 to <0.71	12.0 to <15.0 0.71 to <0.89	≥15.0 ≥0.89

Abbreviations; ALT=alanine aminotransferase; AST=aspartate aminotransferase; LLN=lower limit of normal; NA=not applicable; SGOT=serum glutamic oxaloacetic transaminase; SGPT=serum glutamic pyruvic transaminase; ULN=upper limit of normal.

kReminder: An asymptomatic abnormal laboratory finding without an accompanying AE should not be reported to DAIDS in an expedited time frame unless it meets protocol-specific reporting requirements.

Protocol Amendment 1 ABI-H0731-205

08 September 2020

---

 Reminder: Choose the method that selects for the higher grade.

m Use the applicable formula (ie, Cockcroft-Gault in mL/min or Schwartz, MDRD, CKD-Epi in mL/min/1.73m^2). Sites should choose the method defined in their study and when not specified, use the method most relevant to the study population.

n To convert a magnesium value from mg/dL to mmol/L, laboratories should multiply by 0.4114.

Laboratory Values: Hematology				
Parameter	Grade 1 Mild	Grade 2 Moderate	Grade 3 Severe	Grade 4 Potentially Life-Threatening
Absolute CD4+ Count, Low (cell/mm  ; cells/L) (not HIV infected)	300 to <400 300 to <400	200 to <300 200 to <300	100 to <200 100 to <200	<100 <100
Absolute Lymphocyte Count, Low (cell/mm  ; cells/L) (not HIV infected)	600 to <650 0.600×10  to <0.650×10 	500 to <600 0.500×10  to <0.600×10 	350 to <500 0.350×10  to <0.500×10 	<350 <0.350×10 
Absolute Neutrophil Count (ANC), Low (cells/mm  ; cells/L)	800 to 1,000 0.800×10  to 1.000×10 	600 to 799 0.600×10  to 0.799×10 	400 to 599 0.400×10  to 0.599×10 	<400 <0.400×10 
Fibrinogen, Decreased (mg/dL; g/L)	100 to <200 1.00 to <2.00 OR 0.75 to <1.00×LLN	75 to <100 0.75 to <1.00 OR ≥0.50 to <0.75×LLN	50 to <75 0.50 to <0.75 OR 0.25 to <0.50×LLN	<50 <0.50 OR <0.25×LLN OR Associated with gross bleeding
Hemoglobin o, Low (g/dL; mmol/L) n Male only	10.0 to 10.9 6.19 to 6.76	9.0 to <10.0 5.57 to <6.19	7.0 to <9.0 4.34 to <5.57	<7.0 <4.34
Hemoglobin p, Low (g/dL; mmol/L) n female only	9.5 to 10.4 5.88 to 6.48	8.5 to <9.5 5.25 to <5.88	6.5 to <8.5 4.03 to <5.25	<6.5 <4.03
INR, High (not on anticoagulation therapy)	1.1 to <1.5×ULN	1.5 to <2.0×ULN	2.0 to <3.0×ULN	≥3.0×ULN
Methemoglobin (% hemoglobin)	5.0 to <10.0%	10.0 to <15.0%	15.0 to <20.0%	≥20.0%
PTT, High (not on anticoagulation therapy)	1.1 to <1.66×ULN	1.66 to <2.33×ULN	2.33 to <3.00×ULN	≥3.00×ULN
Platelets, Decreased (cells/mm  ; cells/L)	100,000 to <125,000 100.000×10  to <125.000×10 	50,000 to <100,000 50.000×10  to <100.000×10 	25,000 to <50,000 25.000×10  to <50.000×10 	<25,000 <25.000×10 
PT, High (not on anticoagulation therapy)	1.1 to <1.25×ULN	1.25 to <1.50×ULN	1.50 to <3.00×ULN	≥3.00×ULN
WBC, Decreased (cells/mm  ; cells/L)	2,000 to 2,499 2.000×10  to 2.499×10 	1,500 to 1,999 1.500×10  to 1.999×10 	1,000 to 1,499 1.000×10  to 1.499×10 	<1,000 <1.000×10 

o Male and female sex are defined as sex at birth. For transgender subjects who have been on hormone therapy for more than 6 consecutive months, grade hemoglobin based on the gender with which they identify (ie, a transgender female should be graded using the female sex at birth hemoglobin laboratory values).

p The most commonly used conversion factor to convert g/dL to mmol/L is 0.6206. For grading hemoglobin results obtained by an analytic method with a conversion factor other than 0.6206, the result must be converted to g/dL using appropriate conversion factor for the particular laboratory.

Protocol Amendment 1 ABI-H0731-205

08 September 2020

Laboratory Values: Urinalysis				
Parameter	Grade 1 Mild	Grade 2 Moderate	Grade 3 Severe	Grade 4 Potentially Life-Threatening
Glycosuria (random collection tested by dipstick)	Trace to 1+ or $\leq 250$ mg	2+ or $>250$ to $\leq 500$ mg	$>2+$ or $>500$ mg	NA
Hematuria (not to be reported based on dipstick findings or on blood believed to be of menstrual origin)	6 to $<10$ RBCs per high power field	$\geq 10$ RBCs per high power field	Gross, with or without clots OR with RBC casts OR Intervention indicated	Life-threatening consequences
Proteinuria (random collection tested by dipstick)	1+	2+	3+ or higher	NA

Abbreviations: NA=not applicable; RBC=red blood cells

## **APPENDIX 4 PREGNANCY PRECAUTIONS AND THE DEFINITION OF CHILDBEARING POTENTIAL AND CONTRACEPTIVE REQUIREMENTS**

### **Pregnancy Precautions**

Embryofetal development studies with ABI-H0731 have not been conducted in animals, therefore effects of ABI-H0731 on pregnancy are unknown. Contraceptive requirements for female subjects of childbearing potential are required as described below.

### **Definition of Female Subjects of Childbearing Potential**

A female subject is considered of childbearing potential following menarche and until becoming postmenopausal unless permanently sterile (see below).

If fertility is unclear (eg, amenorrhea in adolescents or athletes) and a menstrual cycle cannot be confirmed before first dose of study drug, additional evaluation should be considered.

Female subjects in the following categories are not considered of childbearing potential

- Premenopausal with one of the following:
  - Documented hysterectomy
  - Documented bilateral salpingectomy
  - Documented bilateral oophorectomy
- Postmenopausal: A postmenopausal state is defined as no menses for 12 months without an alternative medical cause.
- A high FSH level in the postmenopausal range may be used to confirm a postmenopausal state in women not using hormonal contraception or hormonal replacement therapy (HRT). However, in the absence of 12 months of amenorrhea, confirmation with more than 1 FSH measurement is required.
- Females on HRT and whose menopausal status is in doubt will be required to use one of the non-estrogen hormonal highly effective contraception methods if they wish to continue their HRT during the study. Otherwise, they must discontinue HRT to allow confirmation of postmenopausal status before study enrollment.

For individuals with permanent infertility due to an alternate medical cause other than the above, (eg, Müllerian agenesis, androgen insensitivity), Investigator discretion should be applied to determining study entry.

Documentation to determine childbearing potential can come from the site personnel's review of the subject's medical records, medical examination, or medical history interview.

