### 5.2. Inclusion Criteria

Subjects must meet all of the following inclusion criteria in order to be eligible for enrollment:

1. Willing and able to provide informed consent
2. Male or female between the ages 18 and 65 years (inclusive)
3. Body mass index (BMI) 18 to 36 kg/m^2 and a minimum body weight of 45 kg (inclusive)
4. Female subjects of child-bearing potential ([Appendix 4](#)) must be non-pregnant and have a negative serum pregnancy test at Screening and a negative urine pregnancy test predose on Day 1.
5. HBeAg positive or HBeAg negative CHB Chronic hepatitis B infection, defined as HBV infection documented for  $\geq 12$  months.
6. HBV DNA  $>LLOQ$  (using a commercially available assay with  $LLOQ=20$  IU/mL) from 2 samples drawn on 2 separate occasions during the Screening period approximately 10-14 days apart. If the results from these 2 samples indicate a decline in HBV DNA then a third sample will be collected at least a week later for Sponsor review and approval prior to randomization.
7. On a stable NrtI regimen (ETV, TDF, or TAF) for more than 12 months, without evidence of resistance and while known to be adherent to therapy
8. Lack of cirrhosis or advanced liver disease as documented by the following:
  - Liver biopsy results of METAVIR F0-F3 (absence of cirrhosis) within 1 year of Screening
  - OR
  - Fasting FibroScan®  $\leq 14$  kPa within 3 months of Screening (including the Screening visit) or other Sponsor-approved hepatic imaging method within 6 months of Screening indicating lack of cirrhosis (F0 to F3 or equivalent).

If the results from both liver biopsy and FibroScan are available, then the diagnostic method reporting the most advanced liver disease will be used to determine eligibility for the study.
9. Agreement to comply with protocol-specified contraceptive requirements (Refer to [Appendix 4](#)).
10. Agreement to abstain from alcohol abuse (defined as alcohol consumption exceeding 2 standard drinks per day on average (1 standard drink=14 grams of alcohol) and the use of illicit substances from Screening through the duration of the study

11. In good general health, except for CHB (in the opinion of the Investigator)
12. Have the ability to take oral medication and, in the opinion of the Investigator, be willing to adhere to study treatment

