### **6.4.1. Prohibited Concomitant Therapy**

Systemic (oral, injectable, or implanted) hormonal birth control is not permitted as an acceptable means of contraception for female subjects of child-bearing potential. Additional details on acceptable means of contraception are provided in [Appendix 5](#).

Since ABI-H0731 is a weak inhibitor of cytochrome P450 (CYP) 2C9, concomitant use with narrow index CYP2C9 substrates such as warfarin and phenytoin are prohibited. Use of other CYP2C9 substrates should be avoided. Those taking sulfonylureas for controlled diabetes mellitus should monitor blood sugar levels and adjust dosage as appropriate. To the extent possible, other medications with narrow therapeutic indices should be avoided.

The route of elimination in humans is not fully understood so inhibitors and inducers of CYP3A4 should be avoided. Refer to [Appendix 5](#) for details on prohibited CYP2C9 substrates as well as inhibitors and inducers of CYP3A4.

Provisions regarding concomitant medications described in the respective NrtI product labeling must also be followed during the study through the end of the follow up period.

The designated Medical Monitor may be consulted for any questions regarding acceptable or prohibited concomitant medication use during the study. As previously described, concomitant medications, over-the-counter medications, and supplements must be recorded in the subject's source documentation.

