### **Contraceptive Requirements**

The drug-drug interaction (DDI) study with ABI-H0731 and oral contraceptive has not been completed, and therefore, oral contraceptives are not acceptable as a form of effective birth control.

Female subjects of childbearing potential (defined above) must agree to use dual effective birth control methods for the duration of the study and follow-up. Effective birth control methods include male or female condom (may not be used together due to increased risk of breakage), vasectomy, tubal

Protocol Amendment 1 ABI-H0731-205  
08 September 2020

---

sterilization, intrauterine device (IUD), diaphragm, or cervical cap. Note that the DDI of ABI-H0731, and systemic (oral/injectable) hormonal birth control has not been assessed and so systemic hormonal birth control is not considered effective birth control method for female subjects for the purposes of this study. Female subjects must have a negative serum pregnancy test at Screening and a negative urine pregnancy test prior to receiving the first dose of study drug at Baseline (Day 1).

All male subjects must agree to use dual effective birth control methods with their female partners if they are of childbearing potential for the duration of the study and follow-up. In this case, effective birth control methods include systemic (oral/injectable) hormonal birth control, male or female condom (may not be used together due to increased risk of breakage), vasectomy, tubal sterilization, IUD, diaphragm, or cervical cap.

Male subjects must avoid sperm donation from the time of the first dose of study drug and throughout the study period, and for at least 30 days after administration of the last dose of study drug.

Protocol Amendment 1 ABI-H0731-205  
08 September 2020

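### The Appendix 4 HRT bullet steers women of uncertain menopausal status to hormonal contraception that the protocol bars elsewhere, and blurs which rules apply to them (minor)

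*Combined protocol and SAP*

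**What the plan says.** Inclusion 9 (protocol Section 5.2) makes the contraception rules a condition of entry: "Agreement to comply with protocol-specified contraceptive requirements". Those rules are in Appendix 4.

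Under the definition of childbearing potential, Appendix 4 says that women on HRT with uncertain menopausal status "will be required to use one of the non-estrogen hormonal highly effective contraception methods if they wish to continue their HRT during the study". The alternative is to stop HRT so that menopause can be confirmed before enrollment. The bullet follows the line "Female subjects in the following categories are not considered of childbearing potential".

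Three other places restrict hormonal contraception:

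- Section 6.4.1, for women of child-bearing potential: "Systemic (oral, injectable, or implanted) hormonal birth control is not permitted as an acceptable means of contraception".
- Exclusion 14 (Section 5.3), which excludes subjects taking medication prohibited under Section 6.4.1, both before the first dose and throughout the study.
- Appendix 4, Contraceptive Requirements, which reasons from the unassessed interaction with ABI-H0731: "systemic hormonal birth control is not considered effective birth control method for female subjects".

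The same part of Appendix 4 sets the number of methods: "Female subjects of childbearing potential (defined above) must agree to use dual effective birth control methods for the duration of the study and follow-up". Its list of effective methods for women covers condoms and vasectomy, and then tubal "sterilization, intrauterine device (IUD), diaphragm, or cervical cap". The type of IUD is not restricted.

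**The concern.** A site that looks up the HRT bullet finds an instruction to use one estrogen-free hormonal method, with no limit on route. A progestin-type pill, injection or implant meets that instruction. The protocol elsewhere does not permit such a method or does not count it as effective, because its interaction with the study drug is unknown.

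The bullet's position adds to the difficulty. The Section 6.4.1 ban and the dual-method rule are both written for women of childbearing potential. A reader who takes the bullet to describe women outside that group could conclude that neither applies.

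The stake is subject protection. Appendix 4 records that no animal embryofetal studies have been done and that the effect of ABI-H0731 on pregnancy is unknown. The women concerned are those whose fertility has not been settled.

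**Working it through.** The plan gives no figure to reproduce, so the check sets the rules side by side and then makes some simple counts.

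| Rule | Whom it covers | Estrogen-free oral, injectable or implanted method | Methods asked for |
|---|---|---|---|
| Appendix 4, HRT bullet | On HRT, menopausal status uncertain, staying on HRT | Not excluded | 1 |
| Section 6.4.1 | Women of child-bearing potential | Not permitted, all 3 routes | not stated |
| Exclusion 14 | All subjects | Barred through the study, via Section 6.4.1 | not stated |
| Appendix 4, note on systemic methods | Female subjects, no further limit | Not counted as effective | not stated |
| Appendix 4, dual-method rule | Women of childbearing potential | Not among the listed methods | 2 |

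**Does the wording conflict?** The bullet's phrase can mean hormonal methods that contain no estrogen, or any method other than an estrogen-based one. On both readings an estrogen-free pill, injection or implant satisfies the bullet, and neither Section 6.4.1 nor the Appendix 4 note exempts estrogen-free products. Of the 3 systemic routes named in Section 6.4.1, the bullet excludes 0. It also refers to highly effective methods, but Appendix 4 has no such list, only effective ones.

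**Is there a way to comply with everything on route?** Yes. On the narrower reading (the method must be hormonal), the only listed method that can qualify is a hormone-releasing IUD. Stopping HRT before enrollment also avoids the conflict. An IUD alone would still be 1 method, against the 2 required of a woman of childbearing potential.

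**Which rules cover her?** The opening sentence of the definition treats a woman as of childbearing potential from menarche until menopause, unless she is permanently sterile. A woman with uncertain status has not been shown to be postmenopausal, so that sentence includes her. The position of the bullet suggests the opposite. The extracted text does not show any indentation in the original, so the bullet may be a note under the postmenopausal entry.

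**What depends on the classification?**

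- Contraception: 1 method or 2, over 96 + 24 = 120 weeks.
- On-treatment pregnancy tests after Day 1, limited to women of child-bearing potential in Sections 7.4 and 7.5: Weeks 2, 4, 8, 12 and 16 (5); Weeks 20 to 44 every 4 weeks (7); Week 48 (1); Weeks 52 to 96 every 4 weeks (12). Total 5 + 7 + 1 + 12 = 25.
- Follow-up: 1 further test, 4 weeks after treatment (Section 7.6).
- Entry tests: Contraceptive Requirements says "Female subjects must have a negative serum pregnancy test at Screening and a negative urine pregnancy test", with no limit to childbearing potential. Inclusion 4, Sections 7.2 and 7.3 and Table 8 do apply that limit, so the text does not settle these tests independently of her classification.

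The tests are at issue only if she is read as not of childbearing potential.

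**The case against.** The strongest reply is that no woman is governed by the bullet alone. The opening rule makes her of childbearing potential, so Section 6.4.1 does not permit her a systemic hormonal contraceptive. Exclusion 14 carries that section's prohibitions through the study. The Appendix 4 note covers female subjects without limit, so it reaches her however she is classified. Section 6.4.1 also names the Medical Monitor for questions about prohibited medication. A bullet that demands contraception because fertility is uncertain can hardly also mean that she is not fertile. The bullet just above it, on FSH testing, is likewise an explanatory note and not a category of women.

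Most of this stands, and it limits the finding. A reader might infer that the protocol permits systemic progestin-type contraception in these women. Read as a whole, it does not. A reader might also infer that 25 on-treatment tests would be lost. That follows only from the less natural reading; on the better one, every test applies. Nor can one say that the Screening and Day 1 tests are secure whatever her status, given the limit in Inclusion 4 and the other sections cited above.

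The reply does not remove the conflicting instruction. The bullet has no cross-reference to the stricter rules, asks for 1 method where they ask for 2, and stands under a heading that points away from them. A site has to combine several sections to find that the most direct text is not the one to follow.

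**Conclusion.** The point holds as a minor inconsistency in subject-protection wording. The HRT bullet sends a site toward a method that Section 6.4.1, Exclusion 14 and Contraceptive Requirements bar or do not count, and its placement obscures which rules apply. On the better reading the stricter rules govern, so this is neither an operative permission nor a contradiction in every case.

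The conclusion rests on two assumptions: that the opening rule of the definition controls her classification, and that the hormonal contraception sentence in Section 6.4.1 is one of the prohibitions to which Exclusion 14 refers.

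The practical weight is low. A woman must be on HRT, have uncertain menopausal status, choose to stay on HRT and choose a systemic method. The documents do not give the size of that group, and nothing in them shows that such a subject existed. The SAP (Section 1) reports early termination with 2 subjects randomized, so the correction matters mainly if this appendix is reused. No endpoint, comparison or analysis is affected.

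**What to change.** Replace the HRT bullet with a statement placed outside the list of women not of childbearing potential. For example: women taking HRT whose menopause has not been established are treated as of childbearing potential until it is confirmed. They must do one of two things:

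- use two effective methods under Contraceptive Requirements, with no systemic hormonal method, and have every pregnancy test scheduled for women of childbearing potential; or
- stop HRT before enrollment so that postmenopausal status can be confirmed.

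The cost is amendment wording. The dual-method rule and the tests are already in the protocol, so no new procedure is needed.

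Two editorial items can be corrected at the same time, though they carry no weight here. Section 7.3 omits the Day 1 serum pregnancy test that Appendix 1 footnote 11 and Table 8 require. Section 6.4.1 refers to Appendix 5 for contraception details that are in Appendix 4.

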### **Contraceptive Requirements**

The drug-drug interaction (DDI) study with ABI-H0731 and oral contraceptive has not been completed, and therefore, oral contraceptives are not acceptable as a form of effective birth control.

Female subjects of childbearing potential (defined above) must agree to use dual effective birth control methods for the duration of the study and follow-up. Effective birth control methods include male or female condom (may not be used together due to increased risk of breakage), vasectomy, tubal

Protocol Amendment 1 ABI-H0731-205  
08 September 2020

---

sterilization, intrauterine device (IUD), diaphragm, or cervical cap. Note that the DDI of ABI-H0731, and systemic (oral/injectable) hormonal birth control has not been assessed and so systemic hormonal birth control is not considered effective birth control method for female subjects for the purposes of this study. Female subjects must have a negative serum pregnancy test at Screening and a negative urine pregnancy test prior to receiving the first dose of study drug at Baseline (Day 1).

All male subjects must agree to use dual effective birth control methods with their female partners if they are of childbearing potential for the duration of the study and follow-up. In this case, effective birth control methods include systemic (oral/injectable) hormonal birth control, male or female condom (may not be used together due to increased risk of breakage), vasectomy, tubal sterilization, IUD, diaphragm, or cervical cap.

Male subjects must avoid sperm donation from the time of the first dose of study drug and throughout the study period, and for at least 30 days after administration of the last dose of study drug.

Protocol Amendment 1 ABI-H0731-205  
08 September 2020

